4.7.2 Pharmacodynamic Parameters

Endpoints for the PD parameter, WBCT, will be calculated for observed and percent-of-baseline values using actual times relative to the end of injection of study drug (ciraparantag or placebo) dose using Phoenix® WinNonlin® 6.3 or SAS® Version 9.3 (SAS Institute, Inc., Cary, North Carolina). All PD endpoints will be derived over the time window from the study drug administration (0 hour) to the last collection time (i.e., 24 hours after the final administration of the study drug).

The following endpoints will be calculated for the PD parameters, WBCT:

- E_{\min} : minimum value over the 2-minute to 24-hour interval
- tE_{\min} : time of E_{\min}
- $E_{\min(0-6h)}$: minimum value over the 2-minute to 6-hour interval post-final dose
- $tE_{\min(0-6h)}$: time of $E_{\min(0-6h)}$
- E_{\max} : maximum value over the 2-minute to 24-hour interval
- tE_{\max} : time of E_{\max}
- ΔE_{\max} : maximum value minus the baseline value (observed only)

TriPLICATE WBCT that will be done pre-apixaban, post-apixaban at 2.75 hrs and post-study drug or placebo at 1 hr, will be used for analyzing the inter-observer variability of WBCT by an ANOVA model with effects for observer and subject. The inter-observer variability will be summarized by treatment and time point.

4.8 Safety Analysis

Safety evaluations will be based on the incidence, intensity, and relatedness of AEs, physical examination findings, ECG parameters, clinical laboratory tests, stroke assessment and vital signs.

Safety variables will be tabulated and presented for all subjects. Adverse events will be summarized by MedDRA system organ class, preferred term and group; physical examination findings will be listed; and change from baseline in clinical laboratory parameters and vital signs parameters will be summarized by group and listed by subject.

4.8.1 Study Product Exposure

Study drug and apixaban administration will be listed by subject, indicating date and time of drug dose. The study drug administration diary entries will be listed for all subjects, as applicable. A summary of the exposure will be presented.

4.8.2 Adverse Events

All clinical AEs occurring after the subject signs the informed consent form (ICF) up to the time of the Follow-up phone call, whether observed by the Investigator or reported by the subject, will be captured. All AEs will be coded and classified according to MedDRA (Version 20.0 or higher). The severity of AEs is judged by the investigator as mild, moderate or severe, and the relationship to study drug is judged by the investigator as related or not related. Severity should be distinguished from seriousness. Severity is a measure of intensity whereas seriousness is classified by the criteria based on the regulatory definitions (refer to the protocol Section 6.10). An AE of severe intensity need not necessarily be classified as serious. AEs occurring after the date and time of the first dose of study drug up to 30 days following the last dose of study drug are considered treatment emergent AEs (TEAEs).

SAEs occurring up to 30 calendar days post treatment should be reported. Any AEs and SAEs that occur after the specified reporting period should also be reported if in the opinion of the investigator, there is a reasonable possibility for a causal association with the study product. The investigator will follow all SAEs until the SAE is resolved, or stabilized (e.g., in the case of persistent impairment), or returned to baseline, if a baseline value is available, or otherwise justified by the investigator in agreement with the sponsor and all relevant data are received.

All TEAEs will be summarized as the number and percentage of subjects by System Organ Class, Preferred Term and treatment. Separate summaries will be created by severity and by relationship to study drug. If the same AE (preferred term) is reported more than once for the same subject, it will only be counted once in the summary table.

For summary tables by severity and relationship to study drug, if the same AE (preferred term) is reported more than once for the same subject, the highest severity grade or the strongest relationship to treatment will be counted in the summary table.

All AEs will be listed, and a flag will indicate if the AE is non-treatment emergent or treatment emergent.

All serious AEs (SAEs) will be listed, and a flag will indicate if the AE is non-treatment emergent or treatment emergent.

All AEs leading to study discontinuation will be listed by subject.

All AEs leading to death will be listed by subject.

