### 1.2.1 PER977-01-001

PER977-01-001 was a phase 1, first in human, double-blind, placebo-controlled, sequential group, two-period, ascending ciraparantag dose study administered alone and in combination with edoxaban in healthy volunteers. The study consisted of two periods: a single intravenous IV injection of 3 mg, 9 mg, 15 mg, 30 mg, 60 mg, 120 mg or 180 mg ciraparantag, respectively (ciraparantag acetate 5, mg, 15, mg, 25 mg, 50 mg, 100 mg, 200 mg, or 300 mg) alone or placebo with serial PK, pharmacodynamic (PD), and safety monitoring. After a one-week washout, a single dose of edoxaban 60 mg was administered followed 3 hours later by a single dose of ciraparantag or placebo at the same dosage as was administered in the first period, and with serial PK, PD, and safety monitoring.

The highest incidence of treatment emergent adverse events (TEAEs) in Period 1 (ciraparantag monotherapy) were in the system organ class (SOC) of general disorders and administration-site conditions (feeling hot; n=14, 24.1%), and in nervous system disorders (dysgeusia; n=8, 13.8%). Adverse events in placebo subjects comprised feeling cold, headache, infusion related reaction and peripheral coldness reported in one subject each.

The highest incidence of TEAEs in Period 2 was in the SOC of general disorders and administration-site conditions (feeling hot n=11, 17.2%), nervous system disorders (dysgeusia n=8, 12.5%), and in injury, poisonings, and procedural complications (contusion n=7, 10.9%). Adverse events in placebo subjects comprised feeling cold chest discomfort, infusion site coldness, vessel puncture site pain, dysgeusia, headache, contusion, infusion related reaction, peripheral coldness, and hematoma reported in one subject each.

No serious AEs were reported during the conduct of the study, no laboratory results were reported as AEs and there were no clinically significant changes in vital signs. There were no clinically significant AEs and no dose-related findings occurred with regard to interval prolongations in median of triplicate ECG tracings with regard to HR, P-R, QRS, QTcF or R-R intervals.

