**6.10 Adverse Events Assessments**

All AEs and SAEs will be captured by electronic data capture (EDC).

All AEs occurring after the subject signs the ICF up to the time of the Follow-up phone call, whether observed by the Investigator or reported by the subject, will be captured. If in the opinion of the Investigator or the sponsor, an AE meets the criteria of an SAE it is to be reported. SAEs occurring up to 30 calendar days post treatment should be reported. Any AEs and SAEs that occur after the specified reporting period should also be reported if in the opinion of the investigator, there is a reasonable possibility for a causal association with the study product. Medical conditions (including laboratory values/vital signs that are out of range) that were diagnosed or known to exist prior to Informed Consent will be recorded as part of medical history. All SAEs are to be reported according to the procedures in Section [6.10.10](#) SAE Reporting-Procedure for Investigators. Report diagnosis as the AE or SAE term; when the diagnosis is unavailable, report signs and symptoms as individual entries of AE or SAE until the

diagnosis becomes available. For events that are serious due to hospitalization, the reason for hospitalization must be reported as the serious adverse event (diagnosis or symptom requiring hospitalization). A procedure is not an AE or SAE, but the reason for the procedure may be an AE or SAE. Pre-planned (prior to signing the Informed Consent Form) procedure or treatment requiring hospitalization for pre-existing conditions which do not worsen in severity should not be reported as SAEs. For deaths, the underlying or immediate cause of death should always be reported as an SAE. In addition, any serious, untoward event that may occur subsequent to the reporting period that the Investigator assesses as related to study drug should also be reported and managed as an SAE.

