## 7 STUDY ACTIVITIES

A complete schedule of events is provided in the Synopsis.

Where timing for assessments coincide, PD assessments should be performed first, followed by PK assessment(s) as indicated, and then safety measurements.

Time 0 for PK and PD assessments and post-study drug procedures will be the end of the study drug injection.

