#### 7.2.4 Day 4 Procedures

##### 7.2.4.1 Pre-study drug

The following activities and/or assessments will be performed on Day 4 before administration of study drug in all subjects:

- Administration of a single 10 mg dose of apixaban after breakfast; Maintain fast for 4 hours after the apixaban dosing; Water allowed ad libitum
- An ECG and vital signs
- Blood draw for PK assessment of apixaban and ciraparantag baseline at 2.75 hrs. post-apixaban
- Blood draw for WBCT measurement (triplicates post-apixaban at 2.75 hrs.)
- Blood draw for experimental safety biomarker assessment
- Randomization
- AEs and concomitant medications will be recorded
- Stroke assessment at approximately 3 hours post-apixaban dose on the morning ( $\pm 1$ -hour window)

##### 7.2.4.2 Study Drug Administration: Time 0

The following activities and/or assessments will be performed in the order listed on Day 4 in all subjects:

- Vital signs prior to study drug
- I.V. administration of study drug (ciraparantag or placebo)
- AEs and concomitant medications will be recorded

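### The SAP's definition of a treatment-emergent AE has no clause for worsening and does not say whether dose time is the start or the end of the injection

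*SAP*

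**What the plan says.** SAP 4.8.2 holds the only definition of a treatment-emergent AE in the two documents: "AEs occurring after the date and time of the first dose of study drug up to 30 days following the last dose" of study drug. Protocol 3.1 reserves the term study drug for the randomized ciraparantag or placebo, so apixaban does not start the clock. The protocol speaks of treatment-emergent AEs in 6.10.2 and 9.11 but does not define them.

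The AE tables in SAP 4.8.2 rest on this definition: "All TEAEs will be summarized as the number and percentage of subjects by System Organ Class, Preferred Term and treatment". It adds: "Separate summaries will be created by severity and by relationship to study drug". Everything else goes to a listing: "All AEs will be listed, and a flag will indicate if the AE is non-treatment emergent or treatment emergent".

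On timing, Protocol 5.1 gives the injection a minimum length of 10 minutes. Protocol 7 states: "Time 0 for PK and PD assessments and post-study drug procedures will be the end of the study drug injection". Protocol 6.9 says the same for PK and PD, and SAP 4.7.2 also times PD from the end. Protocol 9.9 times the PD parameters from the start. SAP 4.8.1 lists one date and clock time per dose and does not say which end of the injection it marks.

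On collection, Protocol 6.10 captures "All AEs occurring after the subject signs the ICF up to the time of the Follow-up phone call". It asks for SAEs up to 30 days after treatment, and for any later AE or SAE that the investigator thinks may be related.

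**The concern.** The definition has one test, which is when the event occurs relative to the study drug dose. Two kinds of event can fail that test although they belong in a safety comparison of ciraparantag with placebo.

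The first is an event that begins during the apixaban run-in, such as a bruise or a headache, and becomes more severe after the injection. The second is a reaction that begins while the injection is still running, if the recorded dose time is its end.

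SAP 4.8 bases the safety evaluation on the incidence, intensity and relatedness of AEs among other measures, and SAP 4.8.2 tabulates all three on TEAEs. Events that fail the test would be left out of those tables.

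**Working it through.** The plan states no figure on this point, so there is none to reproduce. The check applies the rule as written and asks which events it drops.

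1. **Group sizes** (Protocol 3.1). 3 cohorts × 16 = 48 subjects. At 3:1, each cohort has 12 active and 4 placebo, giving 36 active and 12 pooled placebo. One subject in a dose group moves an incidence by 1/12 = 8.3 percentage points.

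2. **Exposure before study drug** (Protocol 3.1). 2 apixaban doses × 3 days + 1 on Day 4 = 7 doses, in both arms. AEs are captured from consent, so events with onset before the injection will be on record in both arms.

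3. **The rule applied to a 10-minute injection**, reading the SAP's condition as onset strictly after dose time:

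| Onset, minutes from start of injection | Dose time = start | Dose time = end |
|---|---|---|
| Before injection, worsens after it | not a TEAE | not a TEAE |
| 0 | not a TEAE | not a TEAE |
| 5 | TEAE | not a TEAE |
| 10 | TEAE | not a TEAE |
| 12 | TEAE | TEAE |

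The worsening row fails under either clock. The rows at 5 and 10 minutes depend entirely on which clock is used.

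4. **Which clock.** Protocol 6.9, Protocol 7 and SAP 4.7.2 use the end of injection; Protocol 9.9 uses the start. None of these passages governs AE classification, and SAP 4.8.2 does not choose. A programmer could defend either.

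5. **Which arm.** Gap one can arise in either arm, because everyone takes apixaban. For gap two the earlier studies point to the active arms. After unfractionated heparin, feeling hot was reported in 20/48 = 41.7% on ciraparantag and in none on placebo (Protocol 1.2.2). After enoxaparin, related flushing was reported in 9/32 = 28.1% against 0/8 (Protocol 1.2.3, Table 2).

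6. **Size.** For gap two, if dose time is the end:

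   expected subjects dropped per dose = 12 × reaction rate × share with onset during the injection.

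   The share is not in the documents, so it is an assumption that can run from 0% to 100%. Taking related flushing in Table 2 at two of the planned doses:
   - 60 mg: 1/8 = 12.5%; 12 × 0.125 = 1.5, so 0 to 1.5 subjects.
   - 120 mg: 3/8 = 37.5%; 12 × 0.375 = 4.5, so 0 to 4.5 subjects.

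   Each rate comes from eight subjects given a different anticoagulant, and Table 2 has no 30 mg group. The range runs from none to all of these reactions, so it is not an estimate. For gap one the documents give no rate of worsening to put in.

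**The case against.** The strongest reply is that this is a matter of wording. The SAP says occurring, not starting. A worsening entered as a new AE would qualify, and SAP 4.8.2 expects that the same preferred term may be reported more than once in a subject, counting the highest severity. That is true, but no rule tells the site to re-enter a worsened event, and the highest-severity rule works only on events already in the table. SAP 4.8 also says in general terms that AEs will be summarized, without restricting this to TEAEs. It is therefore not established that such an event would appear in no summary at all; what is established is that it would be missing from the TEAE tables. It would still be listed.

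On gap two, Time 0 is defined for PK, PD and post-dose procedures, not for AEs, and Protocol 7.2.4.2 has AEs recorded at the administration step itself. If dose time is the start of injection, the gap all but closes: only an onset in the recorded starting minute is excluded. The eCRF is not among the documents and may already hold both times. This stands, and it is why gap two is stated conditionally.

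A reader might go further in three ways that the documents do not support:
- *That both gaps flatter ciraparantag.* Only the injection-period gap has a direction. Nothing shows that events begun on apixaban worsen more often on ciraparantag.
- *That the 30-day window is empty after the Day 7-10 call and a 3-6 day incidence will pass as a 30-day one.* Routine follow-up does end 3 to 6 days after dosing (7 − 4 = 3; 10 − 4 = 6). But SAEs to 30 days and later possibly related AEs remain reportable, and neither document promises a 30-day incidence. Ending the TEAE window at the call would remove those late events from the tables.
- *That several subjects per dose will be lost.* The 41.7% pools 60 to 360 mg, and the 24.1% for feeling hot in Protocol 1.2.1 is from ciraparantag alone (17.2% after edoxaban). The contusion figure there ("contusion n=7, 10.9"%) is a rate of TEAEs, not of bruises that began earlier and then worsened.

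**Conclusion.** The point holds as two separate gaps. The missing worsening clause is a definite omission: whichever dose time is used, an AE begun on apixaban that worsens after study drug is not a TEAE as written unless it is re-entered. It can affect either arm. The undefined dose time is a conditional one: it matters only if the end of injection is used, and any loss would then fall mainly on the active arms.

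This rests on reading occurring as onset, which is the natural reading. How many subjects are affected cannot be computed, because the documents give neither onset times nor a rate of worsening. With 12 active subjects per dose, each one misclassified moves an incidence by 8.3 percentage points. The primary WBCT analysis is untouched. The gap is worth closing because the safety tables depend on it and the remedy is small.

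**What to change.** In SAP 4.8.2, define a TEAE as an AE with onset at or after the start of the study drug injection, or present before it and worsening in severity after it. Name the time variable that marks the start, and say how missing onset times are handled.

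Have any increase in severity after study drug recorded, so that the flag can be derived, and record the start time of the injection if the eCRF does not already do so. If the eCRF can no longer change, the SAP wording still settles the clock, and the report should say how far worsening could be identified.

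Keep the 30-day upper limit so that late SAEs and late related AEs still count. Add a footnote to the TEAE tables that routine collection of non-serious AEs ends at the Day 7-10 call.

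The cost is a short SAP edit, minor data-entry work and a slightly higher reported TEAE count. Design and dosing do not change.

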4.8.3 Clinical Laboratory Assessments

Blood and urine samples for safety laboratory tests will be collected at screening, at check-in, and prior to discharge from the clinical site. Fecal occult blood tests will be only done at check-in, unless deemed necessary by the Investigator throughout the study. Experimental safety biomarker assessment (e.g. D-Dimer, F1.2 tests) will only be performed at the discretion of the Principal Investigator, and will be collected at pre-apixaban (within 1 hr prior to dosing) on Day 1, and at 2.75 and 8 hrs post-apixaban on Day 4.

Clinical laboratory test parameters (see table in the Protocol Section 6.6.2), with associated reference ranges provided by the laboratory, will be listed for individual subjects. Clinical laboratory test results outside the laboratory's reference ranges will be flagged with "L" for low and "H" for high. Observed values and change from baseline will be summarized by treatment group.

4.8.4 Vital Signs Assessments

Vital signs (blood pressure and heart rate, respiration rate and body temperature) will be measured at screening and check-in and taken after the subject has been supine for 5 minutes. Vital signs will be measured on Day -1, prior to administration of apixaban on the morning of Days 1-4, 30 minutes prior to study drug, at 1.5, 4, 8 and 24 hours post-study drug.

Vital signs results will be listed for each subject, and summary statistics for vital signs and change from baseline will be displayed by treatment.

4.8.5 Resting 12-Lead Electrocardiogram

A resting 12-lead electrocardiogram (ECG) will be performed at screening, after administration of apixaban, and prior to discharge from the clinic site. Parameters assessed will include ventricular rate (bpm), PR interval (msec), QRS duration (msec), QT interval (msec) and QTc interval (msec). Additional ECGs may be performed at the discretion of the Principal Investigator.

All ECG results will be listed by subject and summarized by treatment.

4.8.6 Physical Examinations

A complete physical examination will be performed at screening visit, and an abbreviated physical examination will be performed on check-in and prior to discharge.

Physical examination results will be listed by subject and summarized by treatment.

4.8.7 Stroke Assessments

Stroke assessments will be performed by PI or designee at approximately 3 hours post-apixaban dose on the morning of Day 1 to 4.

Stroke assessment results will be listed by subject.

4.9 Interim Analysis

No interim analyses are planned for this study.

4.10 Statistical Programming and Deliverables

All statistical analyses, tables and listings will be generated in SAS (version 9.3 or later) with appropriate documentation and programming validation. The table of contents of all tables, listings, and figures will be presented in a Tables, Listings and Figures shell supplemental document.

4.11 Changes from Pre-Specified Analyses

In the statistical analysis of complete reversal, Tukey HSD multiple comparison procedure was replaced by one-tailed Dunnett's test for comparison of treatment and placebo means.

4.12 Changes to the Planned Analysis

Any deviation(s) of consequence from the SAP during the data analysis will be documented and justified in an amended SAP and/or in the final report or addressed in a separate document, as appropriate.

Revision history

Version	Date	Comments
0.1 (Draft)	07 November 2017	First draft
0.2 (Draft)	17 November 2017	Second draft per internal comments
0.3 (Draft)	20 December 2017	Updated per sponsor's comments
1.0 (Final)	21 December 2017	Finalization
2.0 (Final)	06 March 2018	Updated per protocol amendment
3.0 (Final)	20 June 2019	Updated per protocol amendment
